### 9.4.1.2 Pharmacokinetic Endpoints

Observed peak and trough plasma concentrations will be measured directly from sparse sampling of plasma concentrations. Secondary PK parameters Cavg, Cmin, Cmax, AUC, and

Tmax will be estimated by population PK analysis and reported separately. An analysis of exposure-response (efficacy and safety) relationship will be conducted as part of the population PK analysis.

# 9.4.1.3 Tertiary/Exploratory Endpoints

The tertiary/exploratory endpoint is the proportion of participants in the APaT population who die at any point from the first dose of study treatment through Study Day 42 and through Study Day 114.

# 9.4.2 Safety Endpoints

The primary safety endpoint is the proportion of participants in the APaT population who experience 1 or more treatment-related AEs during POS study treatment phase (IV or oral) plus 14 days of follow-up.

# 9.4.3 Additional Endpoints

An additional secondary endpoint is participants' categorical perception of the palatability and acceptability of the PFS formulation (Section 8.3.5).

# 9.4.4 Derivations of Efficacy/Immunogenicity/Pharmacokinetics Endpoints

Based on the plasma concentration data obtained within this study, a separate population PK analysis will be performed. The prospective details of this analysis will be specified in a separate Modeling Analysis Plan.

# 9.5 Analysis Populations

# 9.5.1 Efficacy Analysis Populations

The FAS population will serve as the primary population for the analysis of global clinical response data in this study. The efficacy analysis population to be studied (possible, probable, or proven IA) is similar to the population used for the primary efficacy analyses conducted in the adult study (P069) of invasive aspergillosis. The FAS population consists of all allocated participants who:

- have possible, probable, or proven IA (based on modified 2020 EORTC/MSG definitions) as classified by the investigator,
- receive at least 1 dose of study treatment,
- have at least 1 post-allocation observation for the analysis endpoint subsequent to at least 1 dose of study treatment, and
- have baseline data for those analyses that require baseline data.

The Responder Population will serve as the population for the analysis of relapse.

• The Responder Population consists of participants from the FAS population who have achieved a favorable global clinical response at the end of study treatment.

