A small number of studies have provided data regarding recent treatment choices for pediatric patients diagnosed with IA. A 2017 trial of VOR in pediatric participants with IA demonstrated that safety and efficacy outcomes were consistent with previous findings in adult patients [Martin, J. M., et al 2017]. In this 2017 trial, 31 children (14 with proven or probable infection) were enrolled and treated for IA for 6 to 12 weeks. After 6 to 12 weeks of VOR therapy, the global clinical response was 64%. AEs were common, with 30/31 (97%) participants reporting one or more AEs, and 16/31 (52%) of the AEs were considered related to study therapy. In this trial, an association between hepatic AEs and higher VOR exposures was noted, although due to the small sample size, data interpretation was limited. Overall, 48% of participants treated with VOR discontinued therapy early. These results indicate the need to identify alternate therapies for IA that are more efficacious and/or better tolerated.

POS is a highly active triazole with potential advantages in terms of tolerability and drug interactions. POS (IV, PFS, and tablet formulations) has been recently approved for use in children 2 to <18 years of age for the salvage treatment and the prophylaxis of IFIs. This approval was based on data from a prospective PK and safety study that evaluated POS IV and PFS in children 2 to 17 years of age who were at high risk of an invasive fungal infection [Groll, A. H., et al 2020].

The use of newer formulations of POS (PFS, tablet, and IV) provides higher POS concentrations in pediatric patients than the oral suspension formulation and supports the use of the IV formulation in pediatric patients who are unable to tolerate oral dosing. As the newer IV, tablet, and PFS formulations of POS achieve higher POS exposures, the newer formulations have the potential for improved clinical effectiveness.

As immunocompromised pediatric patients are at risk for IA, it is appropriate to study the efficacy and safety of POS IV and oral formulations (PFS and tablets) for the primary treatment of IA in children. This trial evaluates safety, efficacy, and PK of POS IV and oral formulations (PFS and tablets) in pediatric participants 2 to <18 years of age with IA.

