# 7.3 Lost to Follow-up

If a participant fails to return to the clinic for a required study visit and/or if the site is unable to contact the participant, the following procedures are to be performed:

- The site must attempt to contact the participant and reschedule the missed visit. If the participant is contacted, the participant should be counseled on the importance of maintaining the protocol-specified visit schedule.
- The investigator or designee must make every effort to regain contact with the participant at each missed visit (eg, phone calls and/or a certified letter to the participant's last known mailing address or locally equivalent methods). These contact attempts should be documented in the participant's medical record.

Note: A participant is not considered lost to follow-up until the last scheduled visit for the individual participant. The missing data for the participant will be managed via the pre-specified statistical data handling and analysis guidelines.

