# 8.2 Efficacy/Immunogenicity Assessments

# 8.2.1 Global Clinical Response

The investigator will assess global clinical response at the Week 6 and Week 12 visits; in the event of early therapy discontinuation, global clinical response will be assessed at the EOT Visit. All data related to the evaluation of global clinical response will be collected, including clinical signs and symptoms, imaging, serologic testing, and fungal culture and histology. A global clinical response will be assessed by the investigator as favorable (positive) if the participant is alive and has a complete or partial response, using the definitions of responses to therapy and study outcomes in clinical trials of invasive fungal diseases at the time points of interest [Segal, B. H., et al 2008] (Table 6).

Outcome, Response	Definition		
Success			
Complete response	Survival within the prespecified period of observation, resolution of all attributable symptoms and signs of disease, resolution of radiological lesion(s), and documented clearance of infected sites that are accessible to repeated sampling.		
Partial response	Survival within the prespecified period of observation, improvement in attributable symptoms and signs of disease, improvement of radiological lesion(s) a , and evidence of clearance of infected sites that are accessible to repeated sampling. In the case of radiological stabilization b , resolution of all attributable symptoms and signs of fungal disease; or where biopsy of an infected site shows no evidence of hyphae; or where culture is negative.		
Failure			
Stable response	Survival within the prespecified period of observation and minor or no improvement in fungal disease; or persistent isolation of Aspergillus spp or histological present in infected sites.		
Progression of fungal disease	Worsening of clinical symptoms and signs of disease plus new sites of disease or radiological worsening; or persistent isolation of Aspergillus spp from infected sites.		
Death	Death during the prespecified period of evaluation, regardless of attribution.		

a Improvement of radiological lesions is defined as at least 25% reduction in diameter of radiological lesion.

b Radiological stabilization is defined as 0%-25% reduction in the diameter of the lesion.

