# 8.9.2.3 End of Treatment (EOT) Visits

Participants who discontinue study therapy before 12 weeks should have an EOT Visit within 3 days after the EOT. If the EOT Visit falls within the window for a regular scheduled visit, the EOT Visit should occur instead of the scheduled visit and participants should complete all follow-up visits at 14 and 28 days after the last dose.

Every effort should be made, for participants who withdraw consent for participation or who are withdrawn from the study for any reason, to complete the EOT Visit as well as the final mortality assessment at Day 114.

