# 9.6 Statistical Methods

# 9.6.1 Efficacy Analysis

The secondary efficacy endpoint, overall proportions of participants with a favorable global clinical response at Week 6, Week 12, and the EOT Visit, will be estimated and the corresponding 95% CI will be provided using the Clopper-Pearson method [Clopper, C. J. and Pearson, E. S. 1934]. A favorable global clinical response is defined in Section 8.2.1.

In addition, among those who had a favorable global clinical response, the overall proportion of participants who had a relapse of IA through 28 days post-treatment will be provided along with other descriptive statistics.

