### 9.6.3 Safety Analysis

Safety and tolerability will be assessed by clinical review of all relevant parameters including AEs and laboratory parameters. The primary safety analysis will summarize the safety data for participants during the treatment period (IV and oral treatment phases) plus 14 days of

MK-5592-104-04 FINAL PROTOCOL

78

follow-up. Additional safety summaries will be presented in aggregate and by age cohort. No further summary breakdowns by formulations will be performed due to small sample sizes and potential of switching participants back and forth among formulations.

In this descriptive study, the primary safety endpoint of the proportion of participants with drug-related AEs will be provided along with the corresponding 95% CI. The 95% CIs for the safety parameters will be estimated using the Clopper-Pearson method, which is a conservative exact method of providing CIs in this single-arm study.

All other safety parameters will be summarized using descriptive statistics. These include the proportion of participants with the following safety parameters: (1) at least 1 AE; (2) an SAE; (3) a serious and drug-related AE; (4) an AE leading to discontinuation; (5) specific AEs by System Organ Class; and (6) predefined limits of change in specific laboratory parameters. In addition, vital signs, 12-lead ECGs, and standard laboratory safety tests at time points specified in the SoA will be summarized as change from baseline.

The analysis strategy for the safety parameters is summarized in Table 8.

Safety Endpoint	95% CI	Descriptive Statistics			
Any AE		X			
Any SAE		Х			
Any Drug-Related AE	Х	X			
Any Serious and Drug-Related AE		X			
Discontinuation due to AE		X			
Specific AEs, SOCs or PDLCs		X			
Change from Baseline Results (laboratory, ECGs, vital signs)		Х			
Abbreviations: AE=adverse event; CI=confidence interval; ECG = electrocardiogram; PDLC=Predefined Limit of Change; SAE=serious adverse event; SOC=System Organ Class; X=results will be provided.					

Table 8Analysis Strategy for Safety Parameters

Missing values will be handled using the Data-As-Observed approach; that is, any missing values will be excluded from the analysis.

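### FAS entry requires a response observation after dosing, and no rule covers a missing Week 6 or Week 12 response, so unassessed participants can drop out of the single-arm response rate

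*Combined protocol and SAP*

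**What the plan says.** Section 9.5.1 makes the FAS the primary population for global clinical response. Besides an IA classification and at least one dose, members must "have at least 1 post-allocation observation for the analysis endpoint subsequent to at least 1 dose of study treatment".

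Section 9.6.1 estimates the "overall proportions of participants with a favorable global clinical response at Week 6, Week 12, and the EOT Visit" with Clopper-Pearson 95% intervals. It does not say what happens when a response is missing, or whether an EOT result may stand in for Week 6 or Week 12. Sections 9.4.1.1 and 9.4.4 add nothing on either question.

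Section 7.3 says: "The missing data for the participant will be managed via the pre-specified statistical data handling and analysis guidelines". The only such rule in Section 9 closes Section 9.6.3, Safety Analysis: "Missing values will be handled using the Data-As-Observed approach; that is, any missing values will be excluded from the analysis".

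Four other places bear on the point:

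- Section 8.2.1 has the investigator assess response at Week 6 and Week 12, and adds that "in the event of early therapy discontinuation, global clinical response will be assessed at the EOT Visit".
- Table 6 lists under failure: "Death during the prespecified period of evaluation, regardless of attribution".
- Section 8.9.2.3 and the Schedule of Activities require an EOT Visit within 3 days when treatment stops before Week 12. Section 8.9.2.3 adds: "If the EOT Visit falls within the window for a regular scheduled visit, the EOT Visit should occur instead of the scheduled visit".
- Sections 4.1 and 7.1 expect participants who have stopped treatment to complete the remaining visits. The Schedule of Activities places a response assessment at Week 6, Week 12 and EOT.

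**The concern.** Whether a response is recorded is plausibly tied to the outcome. A child who deteriorates, is withdrawn or dies early is less likely to have a completed response assessment than one who is doing well. A denominator limited to assessed participants then loses likely failures, and the rate rises. With one arm, no comparator shares the effect or reveals it.

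Section 9.6.1 does not say whether the safety section's exclusion rule extends to efficacy. If it does, unassessed participants are dropped. If it does not, efficacy has no rule and Section 7.3 points to nothing. Sponsor staff see the open-label data as they accrue (Section 9.2), so a rule settled later would be settled with outcomes in view.

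At stake are the estimate and interval for the secondary efficacy endpoint. There is no hypothesis test to distort. Treatment-related adverse events and all-cause mortality use the All Participants as Treated population.

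**Working it through.** **1. Reproduce the plan's figures.** For x responders among n, the exact two-sided 95% limits are: lower = Beta(0.025; x, n − x + 1), upper = Beta(0.975; x + 1, n − x). With n = 15 as in Table 9:

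- 9/15 = 60.0% [32.3, 83.7]
- 6/15 = 40.0% [16.3, 67.7]
- 3/15 = 20.0% [4.3, 48.1]

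All three rows match.

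**2. Inputs for the illustration.** Section 9.9.2 expects about 30 treated participants. A true rate of 40% (12 of 30) is assumed; it is the middle row of Table 9 and close to the 45% and 42% that Section 9.9.1 cites from the adult and adolescent study. The documents give no rate of missing responses, so 3 and 6 unassessed non-responders are assumed.

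**3. Effect of dropping unassessed non-responders.**

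| Handling | Rate | 95% interval |
|---|---|---|
| All treated, missing not favorable | 12/30 = 40.0% | [22.7, 59.4] |
| 3 unassessed excluded | 12/(30 − 3) = 12/27 = 44.4% | [25.5, 64.7] |
| 6 unassessed excluded | 12/(30 − 6) = 12/24 = 50.0% | [29.1, 70.9] |

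On the plan's basis of 15 with 6 responders, 3 missing and excluded gives 6/12 = 50.0% [21.1, 78.9] against 6/15 = 40.0%.

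**4. Where an EOT result is left without a visit.** The response visit windows are Days 39 to 47 (Week 6) and Days 81 to 89 (Week 12). A participant who stops on Day 42 has the EOT Visit by Day 42 + 3 = Day 45, inside the Week 6 window, so EOT replaces that visit. An EOT Visit before Day 39 or on Days 48 to 80 falls in neither window, and nothing maps its result to Week 6 or Week 12.

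**5. The direction at Week 12 is not fixed.** Planned treatment may end from Day 42, so some participants without a Week 12 assessment may be responders who finished early. Suppose 3 of the 12 responders have only a favorable EOT result:

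- missing counted as not favorable: 9/30 = 30.0% [14.7, 49.4]
- missing excluded: 9/27 = 33.3% [16.5, 54.0]
- EOT result fills Week 12: 12/30 = 40.0% [22.7, 59.4]

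The same 30 children give 30%, 33% or 40%, depending only on a rule that the plan does not state.

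**The case against.** The strongest reply is that the protocol already limits the problem. Sections 4.1 and 7.1 keep participants on the visit schedule after treatment stops, so early stoppers are arguably still due responses at Week 6 and Week 12, and the EOT sentence in Section 8.2.1 can be read as an added assessment. An EOT Visit is required within 3 days of early stopping, and Section 8.1.9 asks for EOT activities at withdrawal, so few treated participants should lack every response observation. Mortality is checked at every visit after Day 1 and through Day 114, and Table 6 makes death a failure. The intervals in the illustration overlap heavily.

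Much of this stands, and it rules out several stronger readings:

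- **That about half the participants could lack a Week 12 response.** A reader might take this from Section 2.1: "Overall, 48% of participants treated with VOR discontinued therapy early". That figure concerns another drug and early stopping, not missing assessments, and Sections 4.1 and 7.1 expect visits to continue.
- **That deaths leave the analysis.** Table 6 points the other way. What is missing is a statement that a death before any assessment meets the observation criterion in Section 9.5.1.
- **That the bias is always upward.** At Week 12 it can go either way, as shown above.
- **That the enrolment targets must change.** The target of 15 already depends on at least 7 days of oral therapy after the end of IV treatment.
- **That EOT should be carried forward in the main analysis.** In the Week 12 example that gives the highest rate (40% against 33% or 30%). Its safeguard, no recorded relapse, is also empty for participants who did not complete treatment, because the Schedule of Activities assesses relapse only after completion.

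The reply does not supply a rule. Attending visits reduces missing responses but does not say how to count those that remain. Section 8.1.9 says only that participants who stop early should be encouraged to continue with visits, and Section 8.2.1 can still be read as putting EOT in place of the later assessments.

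**Conclusion.** The concern holds. As written, the response denominator depends on having an assessment, no missing-response rule is given for efficacy, and the one rule in Section 9 would exclude the unassessed if it were applied. Under the assumed counts, excluding 3 or 6 unassessed non-responders adds 4.4 or 10.0 percentage points to a 40.0% rate. The sizes rest on those assumptions, since the plan states no missing rate. Complete FAS exclusion should be uncommon; the larger gap is at the scheduled visits. The change should be made before results are known, but it concerns a secondary, descriptive endpoint and leaves primary safety and mortality untouched.

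**What to change.** **Section 9.5.1.** For the response analysis, use all treated participants with possible, probable or proven IA, and delete the requirement for an observation after allocation.

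**Section 9.6.1.**

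- Count death on or before the visit as not favorable.
- Count any response still missing at Week 6, Week 12 or EOT as not favorable.
- State that the Data-As-Observed rule in Section 9.6.3 does not govern response.
- Report two sensitivity analyses: the observed-case rate, and a rate in which an EOT result outside the visit window fills that visit. The second is needed because, at Week 12, counting missing as not favorable can misclassify responders who completed early.

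**Sections 8.2.1, 4.1 and 7.1.** Reconcile them so that it is clear whether response is still assessed at Week 6 and Week 12 after treatment stops.

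**Cost.** SAP wording, one protocol clarification and one extra table. No new data are needed, since vital status is already sought through Day 114. The downside is a somewhat lower main estimate.

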# 9.5.2 Pharmacokinetic Analysis Population

The primary PK population for this study will be all treated participants who receive at least 7 days of POS IV solution treatment and have postdose POS PK sampling while on POS IV therapy.

# 9.5.3 Safety Analysis Populations

The APaT population will be used for the analysis of safety data and all-cause mortality in this study. This population consists of all enrolled participants who received at least 1 dose of study treatment, regardless of their IA classification.

# 9.6 Statistical Methods

# 9.6.1 Efficacy Analysis

The secondary efficacy endpoint, overall proportions of participants with a favorable global clinical response at Week 6, Week 12, and the EOT Visit, will be estimated and the corresponding 95% CI will be provided using the Clopper-Pearson method [Clopper, C. J. and Pearson, E. S. 1934]. A favorable global clinical response is defined in Section 8.2.1.

In addition, among those who had a favorable global clinical response, the overall proportion of participants who had a relapse of IA through 28 days post-treatment will be provided along with other descriptive statistics.

# 9.6.2 Pharmacokinetic Analysis

A population PK analysis will be conducted as described in a separate Modeling Analysis Plan based on population PK models developed from prior pediatric and adult PK data. The modeling analysis will be based on actual dose administered, which will account for differences in dosing regimen. Model-predicted individual concentration-time profiles will be used to determine Cmax, Cmin, Cavg, AUC, and Tmax. PK parameters for POS derived from the population PK analysis will be reported in a separate modeling and simulation report. Exposure/response assessments, including an exploration of the relationship between PK/PD indices with efficacy and safety time points, as available data allow, will be conducted as part of the population PK analysis and will also be reported separately.

### 9.6.3 Safety Analysis

Safety and tolerability will be assessed by clinical review of all relevant parameters including AEs and laboratory parameters. The primary safety analysis will summarize the safety data for participants during the treatment period (IV and oral treatment phases) plus 14 days of

MK-5592-104-04 FINAL PROTOCOL

78

follow-up. Additional safety summaries will be presented in aggregate and by age cohort. No further summary breakdowns by formulations will be performed due to small sample sizes and potential of switching participants back and forth among formulations.

In this descriptive study, the primary safety endpoint of the proportion of participants with drug-related AEs will be provided along with the corresponding 95% CI. The 95% CIs for the safety parameters will be estimated using the Clopper-Pearson method, which is a conservative exact method of providing CIs in this single-arm study.

All other safety parameters will be summarized using descriptive statistics. These include the proportion of participants with the following safety parameters: (1) at least 1 AE; (2) an SAE; (3) a serious and drug-related AE; (4) an AE leading to discontinuation; (5) specific AEs by System Organ Class; and (6) predefined limits of change in specific laboratory parameters. In addition, vital signs, 12-lead ECGs, and standard laboratory safety tests at time points specified in the SoA will be summarized as change from baseline.

The analysis strategy for the safety parameters is summarized in Table 8.

Safety Endpoint	95% CI	Descriptive Statistics			
Any AE		X			
Any SAE		Х			
Any Drug-Related AE	Х	X			
Any Serious and Drug-Related AE		X			
Discontinuation due to AE		X			
Specific AEs, SOCs or PDLCs		X			
Change from Baseline Results (laboratory, ECGs, vital signs)		Х			
Abbreviations: AE=adverse event; CI=confidence interval; ECG = electrocardiogram; PDLC=Predefined Limit of Change; SAE=serious adverse event; SOC=System Organ Class; X=results will be provided.					

Table 8Analysis Strategy for Safety Parameters

Missing values will be handled using the Data-As-Observed approach; that is, any missing values will be excluded from the analysis.

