# 8.4.7 Events of Clinical Interest (ECIs)

Selected nonserious and SAEs are also known as ECIs and must be reported to the Sponsor.

Events of clinical interest for this study include:

1. An elevated AST or ALT lab value that is greater than or equal to 3X the upper limit of normal and an elevated total bilirubin lab value that is greater than or equal to 2X the upper limit of normal and, at the same time, an alkaline phosphatase lab value that is less than 2X the upper limit of normal, as determined by way of protocol-specified laboratory testing or unscheduled laboratory testing.\*

\*Note: This section reflects the handling of nonserious ECI. ECI events meeting SAE criteria are to be reported in the same manner as SAE. The purpose of the criteria is to specify a threshold of abnormal hepatic tests that may require an additional evaluation for an underlying etiology. The study site guidance for assessment and follow-up of these criteria can be found in the Investigator Study File Binder (or equivalent).

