# 9.9 Sample Size and Power Calculations

# 9.9.1 Efficacy Analysis

The sample size was chosen based on clinical considerations, not statistical ones. However, of interest is the precision of the estimates of efficacy. The width of the 95% CI for the global clinical response rate will depend on the size of the population and the number of participants who achieve a favorable clinical response. In a study completed in 2019 (P069) in 575 adults and adolescents to study efficacy and safety of POS versus VOR for the treatment of invasive aspergillosis, the favorable global clinical response rates at Week 6 and Week 12 for the participants on POS were 45% and 42%, respectively [Maertens, J. A., et al 2021].

Table 9 summarizes the observed global clinical response rate and the corresponding 95% CI for a variety of observed response rates for a population of 15 participants (the overall evaluable population).

Number of Participants in Population	Number Achieving Clinical Response	Observed Global Clinical Response	95% Confidence Interval a	
	9	60.0%	[32.3, 83.7]	
15	6	40.0%	[16.3, 67.7]	
	3	20.0%	[4.3, 48.1]	
a Confidence intervals are based on the Clopper-Pearson method [Clopper, C. J. and Pearson, E. S. 1934].				

Table 9Summary of Potential Observed Global Clinical Response Rates and95% Confidence Intervals

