### 9.9.2 Safety Analysis

The primary safety analysis will summarize the safety data for participants during the treatment period (IV and oral treatment phases) plus 14 days of follow-up.

The APaT population is expected to include approximately 30 participants. The estimate of and the upper bound of the 95% CI for the underlying percentage of participants with a specific AE, given various hypothetical observed number of participants with that specific

AE within the study, are provided in Table 10. These calculations are based on the exact binomial method proposed by Clopper and Pearson.

Ν	Hypothetical Number of Participants with AE	Estimate of Incidence	95% CI Upper Limit a
	0	0.0%	9.5%
	2	6.7%	22.1%
30	5	16.7%	34.7%
	10	33.3%	52.8%
	15	50.0%	68.7%

Table 10Estimate of Incidence of a Specific AE and Upper Limit of 95% CI Based on aHypothetical Number of Participants with that Specific AE

Abbreviations: AE=adverse event; CI = confidence interval.

a Based on the 2-sided exact 95% confidence interval (CI) on a binomial proportion [Clopper, C. J. and Pearson, E. S. 1934].

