### Assessment of intensity/toxicity

- An event is defined as "serious" when it meets at least 1 of the predefined outcomes as described in the definition of an SAE, not when it is rated as severe.
- The investigator will make an assessment of intensity for each AE and SAE (and other reportable safety event) according to the NCI CTCAE, version 5.0. Any AE that changes CTCAE grade over the course of a given episode will have each change of grade recorded on the AE CRFs/worksheets.
  - Grade 1: Mild; asymptomatic or mild symptoms; clinical or diagnostic observations only; intervention not indicated.
  - Grade 2: Moderate; minimal, local or noninvasive intervention indicated; limiting age-appropriate instrumental ADL.
  - Grade 3: Severe or medically significant but not immediately life-threatening; hospitalization or prolongation of hospitalization indicated; disabling; limiting self-care ADL.
  - Grade 4: Life threatening consequences; urgent intervention indicated.
  - Grade 5: Death related to AE.

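### Table 10 illustrates safety precision by the exact upper limit for a specific AE, but Table 8 plans a confidence interval only for any drug-related AE, and Table 10's zero-event limit is one-sided

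*Combined protocol and SAP*

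**What the plan says.** Safety is the primary objective (section 3). The primary endpoint is the proportion of treated participants with at least one treatment-related AE, up to 14 days after treatment (9.4.2).

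- **Precision (9.9.2, Table 10).** "The APaT population is expected to include approximately 30 participants". The section then tabulates the estimate and "the upper bound of the 95% CI for the underlying percentage of participants with a specific AE" for 0, 2, 5, 10 and 15 affected participants out of 30. On method it says "These calculations are based on the exact binomial method proposed by Clopper and Pearson", and the table footnote adds "Based on the 2-sided exact 95% confidence interval (CI) on a binomial proportion".
- **Analysis (9.6.3, Table 8).** The primary endpoint gets a Clopper-Pearson 95% CI. For the rest: "All other safety parameters will be summarized using descriptive statistics". Table 8 has separate columns for the CI and for descriptive statistics. The CI column is marked in one row, any drug-related AE. It is empty for any AE, any SAE, serious and drug-related AE, discontinuation due to AE, specific AEs/SOCs/PDLCs, and change from baseline.
- **Cohorts.** Section 9.6.3 promises additional safety summaries in aggregate and by age cohort. Section 4.1 plans about 20 and about 10 participants in the two cohorts.
- **Harms singled out elsewhere.** Section 8.4.7 says "Selected nonserious and SAEs are also known as ECIs and must be reported to the Sponsor" and lists one, a combination of raised AST or ALT and raised bilirubin without a matching rise in alkaline phosphatase. Section 2.3 names hepatic toxicity and QTc prolongation among the identified risks, and 7.1 uses a QTc threshold of 500 msec. Section 10.3.5 says "The investigator will make an assessment of intensity for each AE and SAE", using CTCAE version 5.0.
- **Basis of the sample size (9.9.1, and likewise 9.1).** "The sample size was chosen based on clinical considerations, not statistical ones".

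**The concern.** The measure used to show what the trial can say about a specific harm is not among its planned outputs. The one interval that is planned belongs to an endpoint that pools all grades and all event types, so it says little about hepatic, cardiac or other serious harm.

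With about 30 children, the useful statement about a serious harm is how high a rate a low or zero count still allows. A bare 0% is easily read as absence of risk, and more so in a cohort of 10. An event that does not occur may get no row in a specific-AE table at all, so nothing would be said about it.

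A reader who turns to Table 10 to fill the gap finds the wrong number in the zero-event row, the row most relevant here.

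**Working it through.** **Inputs.** N = 30 (9.9.2); cohorts of 20 and 10 (4.1); two-sided 95% Clopper-Pearson (9.6.3, 9.9.2 and the Table 10 footnote).

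**Formula.** For x affected out of n, the two-sided upper limit is the 0.975 quantile of Beta(x+1, n−x). For x = 0 this reduces to 1 − 0.025^(1/n). The one-sided 95% limit uses 0.95 in place of 0.975, which for x = 0 gives 1 − 0.05^(1/n).

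**Step 1: reproduce Table 10 (n = 30).**

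| x | Table 10 | Two-sided 95% upper | One-sided 95% upper |
|---|---|---|---|
| 0 | 9.5% | 11.6% | 9.5% |
| 2 | 22.1% | 22.1% | 19.5% |
| 5 | 34.7% | 34.7% | 31.9% |
| 10 | 52.8% | 52.8% | 49.9% |
| 15 | 68.7% | 68.7% | 66.1% |

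Four rows reproduce as two-sided. The zero row does not: 1 − 0.025^(1/30) = 11.6%, whereas 1 − 0.05^(1/30) = 9.5%. The printed 9.5% is the one-sided limit and conflicts with the footnote. A two-sided zero-event limit of 9.5% would need 37 participants: 1 − 0.025^(1/37) = 9.49%.

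**Step 2: what a CI would show for low counts (two-sided 95%).**

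| x | n = 30 | n = 20 | n = 10 |
|---|---|---|---|
| 0 | 0 to 11.6% | 0 to 16.8% | 0 to 30.8% |
| 1 | 0.1 to 17.2% | 0.1 to 24.9% | 0.3 to 44.5% |
| 2 | 0.8 to 22.1% | 1.2 to 31.7% | 2.5 to 55.6% |
| 3 | 2.1 to 26.5% | 3.2 to 37.9% | 6.7 to 65.2% |

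Under Table 8 as written, the first row would appear as 0% in all three columns, with nothing to separate them.

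**Step 3: how often a real harm gives a zero count in 30.** The probability is (1 − p)^30. At an assumed true rate of 5% it is 0.95^30 = 21%; at 2% it is 0.98^30 = 55%.

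**Step 4: sensitivity to N.** The 30 is approximate. The zero-event two-sided limit is 13.7% at n = 25 and 10.0% at n = 35.

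**Step 5: does the text of 9.6.3 plan more intervals than Table 8?** One sentence refers to the CIs for the safety parameters in the plural. It names a method, not further endpoints. The sentence after it limits everything other than the primary endpoint to descriptive statistics, and Table 8, which keeps the two apart, agrees.

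**The case against.** The plan is coherent on its own terms. It is descriptive, has no hypotheses (9.3), and reserves its one interval for the primary endpoint; 9.1, 9.6.3 and Table 8 agree on this. An exact limit depends only on x and n, both of which will be reported, so anyone can compute it. The ECI has its own expedited reporting (8.4.1, Table 7), and an external DMC reviews interim safety data. Rows for serious drug-related AEs and for discontinuations already separate the more important events from the mild ones. Repeating exact intervals for every specific AE in cohorts of 20 and 10 would produce many very wide, unadjusted intervals.

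Much of this stands. The gap is one of reporting and loses no information, and a blanket CI column for all specific AEs would be the wrong remedy: it adds clutter and still cannot bound an AE that never occurs and so has no row. What does not stand is leaving readers to supply the limit themselves. Table 10 covers only N = 30, gives no lower limits and no cohort values, and is wrong at zero. ECI reporting and DMC review protect participants during the trial, but they do not put a limit in the final tables.

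Stronger readings are tempting, and the documents do not support them:

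- *That Table 10 justifies enrolling 30.* Sections 9.1 and 9.9.1 both say the number was chosen on clinical grounds. Table 10 only illustrates precision.
- *That Table 8 certainly omits the hepatic combination.* It has no named row for it, but the PDLC row might cover it. The documents do not list the PDLC limits, so neither can be asserted.
- *That the ECI and CTCAE grade are recorded for every participant.* Grade is assigned per AE, and the ECI is triggered by a laboratory combination.

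**Conclusion.** The point holds as a mismatch between the illustrated precision and the planned output, together with one numerical error. SAEs, serious drug-related AEs, discontinuations due to AE and zero-event harms of prior interest would be reported without an interval. For a zero count, the missing upper limit is 11.6% overall and 16.8% or 30.8% by cohort. Table 10 understates its own zero-event limit by 2.1 percentage points (11.6 − 9.5).

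These sizes assume that 30, 20 and 10 participants are actually treated, and that every treated participant counts in the denominator. Section 9.6.3 excludes missing values, so laboratory and ECG denominators could be smaller and the limits higher.

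The primary estimate, the sample size and the safety reporting rules are unaffected. The change is worth making because safety is the primary objective and the cost is small.

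**What to change.** 1. In 9.6.3 and Table 8, mark the Clopper-Pearson 95% CI for any SAE, any serious and drug-related AE, and discontinuation due to AE.
2. Add a short prespecified list of harms reported with n, denominator, % and 95% CI even when the count is zero: the hepatic ECI of 8.4.7, QTc above 500 msec, and drug-related AEs of CTCAE grade 3 or higher. Show these overall and by age cohort. Leave the other specific AEs descriptive.
3. In Table 10, change the zero-event limit from 9.5% to 11.6%, so that it matches the footnote and the other four rows.
4. Reword the sentence on CIs for the safety parameters to name the rows it covers.

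The cost is SAP wording, three more marked rows and three added ones, with no new data collection. The downside is a few more wide, unadjusted intervals, which is acceptable in a descriptive trial that plans no multiplicity adjustment (9.8), provided they are labelled as descriptive.
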